## 6.7 STUDY METHODOLOGY

Participants will be taken to the procedure room. Local anaesthesia will be injected into diseased hair-bearing area on affected axillae or groin on both sides. FUE will be performed by the investigator (who is experienced in FUE) using 0.8/0.9/1.0 mm Ertip® punch. The extracted hair follicular unit samples will be analysed histologically to confirm complete removal of the pilosebaceous units. Specimens are not kept for future analysis as they will be discarded.

At each study visit, the dermatologist will count the number of abscesses and nodules (as part of standard routine care) and will document this in their medical record. This will help to also score the HiSCR, IHS4, HS-PGA4 and participants will ask to rate their pain using the numerical pain score. Scoring will be done by the principle investigator as well as another dermatologist at Sinclair Dermatology.

Participants will be given a sheet (Appendix 3) where they can complete a diary of whenever they have a flareup which will identify the date of the flareups, which side and their pain level. This will be reviewed at each study visit.

Biospecimens are not kept by the investigators and are discarded once reviewed to confirm removal of pilosebaceous units.

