## 2. STUDY SYNOPSIS

Provide brief information

Title:	Hidradenitis suppurativa treated with follicular unit excision: A prospective controlled pilot study
Short Title:	Hidradenitis suppurativa treated with follicular unit excision: A prospective controlled study
Design:	Open-label, interventional
Study Centres:	Sinclair Dermatology, Melbourne Australia
Hospital:	
Study Question:	How effective is follicular unit excision for the treatment of mild-moderate hidradenitis suppurativa?
Study Objectives:	
Primary Objectives:	The study's primary objective is to determine change in several hidradenitis suppurativa assessment scores score throughout follow-up visits in the first 24 weeks after follicular unit excision
Secondary Objectives	
 
i) To compare the changes in Hidradenitis Suppurativa assessment scores between intervention and control groups up to 24 weeks and on the treated sites before and after follicular unit extraction
 
ii) To compare the number of disease flares between the treated and control groups for 24 weeks after treatment
 
iii) To determine if specimens contain hair follicles, sebaceous glands, apocrine glands and eccrine glands on histopathology
 

Key Inclusion Criteria:	
 
i) Patients aged <math>\geq 18</math> years with hidradenitis suppurativa
 
ii) Mild-moderate hidradenitis suppurativa defined by Hurley stage 1 up to 2A
 
iii) Minimum diagnosis of 3 months prior to baseline
 
iv) Active hidradenitis suppurativa present for <math>\geq 3</math> months from initial diagnosis
 

Key Exclusion Criteria:	
 
i) Current treatment with systemic antibiotics, retinoids, immunosuppressants or biologic agents at discretion of the investigator
 
ii) Extensive scarring
 
iii) Absence of terminal hairs in target areas
 
iv) Previous laser hair removal in target areas
 
v) Pregnant or lactating women
 

Number of Planned Participants :	24
Investigational procedure:	Follicular unit excision using 0.8 mm Ertip® punch
Data analysis	The primary objective is to evaluate the efficacy of follicular unit excision in the treatment of adults with mild to moderate hidradenitis suppurativa. The primary analysis will be conducted to assess the primary and secondary endpoints once all participants have completed the Week 24 visit.
Safety considerations:	

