Follicular unit excision (FUE) is a minimally invasive surgical technique used in hair transplantation surgery where hair grafts are extracted from the donor area and implanted in the recipient area under local anaesthesia. Although grafts are usually harvested from the back and sides of the scalp, other donor sites include the beard, chest and other parts of the body. In FUE, the skin around a follicular unit is scored using a 0.8-1 mm circular punch mounted on a motorized hand device, and the graft is subsequently extracted. The extraction leaves a wound which heals by secondary intention. Residual scars are pin-point dots which are virtually imperceptible to the naked eye.

Although FUE is mostly used in hair transplantation, it has been used for other dermatological indications. Notably, extraction of pigmented hair grafts and placement into depigmented skin in patients with stable vitiligo resulted in skin re-pigmentation. This is likely due to migration of follicular melanocytes to vitiliginous skin.

Laser hair removal has been shown to be effective in reducing flares and severity of HS. In addition, deroofing with carbon dioxide laser with hair follicle removal using a neodymium-doped yttrium aluminum garnet (Nd:YAG) laser has been shown to reduce recurrence rates. Even in mild HS, Nd:YAG laser hair depilation increased patient satisfaction and reduced mean HS severity score.

To our knowledge, FUE to treat HS has not been attempted. Apocrine and eccrine glands are known to reside next to HFs. Given that HFs and/or apocrine glands are central to the pathophysiology of HS, and that laser hair removal has been shown to be an effective treatment, we propose that FUE can be an effective treatment modality for HS. In contrast to laser hair removal, FUE would also remove apocrine glands. In addition, hair removal using laser is often temporary, with hair regrowth occurring within a few months if laser treatment is not maintained. On the other hand, FUE would result in permanent removal of HFs and associated apocrine glands, thereby offering a more long-lasting solution.

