#### 6.4.1.6 MANAGEMENT OF FLAREUPS

Participants may be given medications to prevent flares to stabilize the condition prior to follicular unit extraction. This may be resorcinol 15% cream and/or oral antibiotics such as doxycycline 100mg. Often, flareups may need surgical management or intralesional corticosteroids. These are given as part of standard routine care to minimize flare-ups for the hidradenitis suppurativa and alleviate symptoms for patients and is part of management guidelines.

Participants may be given a sheet to document their flareups (Appendix 3). Participants may take photos of the flareups on their phone to show to the investigator but this is optional only. Investigators will not be collecting photos taken by participants.

Participants are divided into the intervention group and control group. The control group will be managed with topical clindamycin. A staff member of Sinclair Dermatology not involved in this study will randomise participants into the intervention and controlled group using the program from [www.randomizer.org](http://www.randomizer.org) in a 1:1 stratification ratio. The treatment group will be treated with follicular unit extraction. Due to the study design (the intervention being surgical and the controlled group being a topical application), investigators and participants are unable to be blinded as to which participants will be in the treatment or control group. As there will be 24 participants in this study, numbers 1-24 will be randomly allocated to either control or treatment group using [randomizer.org](http://randomizer.org) prior to recruitment of the study. Participants will then be allocated a number in the order in which they are recruited in the study and subsequently will be placed in the group that the number has been randomised into.

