## 6.6 RANDOMISATION

A staff member of Sinclair Dermatology not involved in this study will randomise participants into the intervention and controlled group using the program from [www.randomizer.org](http://www.randomizer.org) in a 1:1 stratification ratio. The treatment group will be treated with follicular unit extraction. Due to the study design, investigators and participants are unable to be blinded as to which participants will be in the treatment or control group. As there will be 24 participants in this study, numbers 1-24 will be randomly allocated to either control or treatment group using [randomizer.org](http://randomizer.org) prior to recruitment of the study. Participants will then be allocated a number in the order in which they are recruited in the study and subsequently will be placed in the group that the number has been randomised into.

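### No masking is provided for either lesion scorer, although a second dermatologist is already planned and could score without being told the arm

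*Protocol*

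**What the plan says.** The synopsis (Section 2) describes the design as "Open-label, interventional". Section 6.6 says that "investigators and participants are unable to be blinded as to which participants will be in the treatment or control group". Section 6.4.1.6 repeats this and gives the reason: "the intervention being surgical and the controlled group being a topical application".

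Scoring is assigned in Section 6.7: "Scoring will be done by the principle investigator as well as another dermatologist" at the same clinic. The same section has the dermatologist count abscesses and nodules at each visit, and these counts feed HiSCR, IHS4 and HS-PGA. It identifies the operator for FUE only as the investigator.

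No section says what the second dermatologist knows about allocation, separates that person from treatment, or masks either scorer. On how visible the treated sites are, Section 5.3 says of FUE in general: "Residual scars are pin-point dots which are virtually imperceptible to the naked eye". It also says that the follicles are removed permanently.

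**The concern.** The protocol treats blinding as one question, answers it for the people who give and receive treatment, and stops. Who assesses the outcome is a separate question. A trial in which operator and participant must know the arm can still have a rater who is not told it.

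This matters because the physician-rated outcomes depend on judgement: whether a lesion is inflammatory, and whether it is a nodule, an abscess or a draining tunnel. The hypothesis in Section 6.1 compares FUE with topical treatment on these scores. A tendency to grade one arm more leniently would enter that comparison directly and could not be told apart from a treatment effect. Sections 9.1 and 9.2 also say that the results will be used to size later studies, so a distorted difference would carry forward.

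An analysis plan cannot repair this afterwards, because what the assessor knew at a visit is fixed once the visit has taken place.

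**Working it through.** The protocol has no figure of its own to reproduce on this point: it states no alpha, power, effect size or standard deviation. The check is a reading of the text, followed by illustrations under stated assumptions.

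**Text, role by role**

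| Role | What the protocol says about knowledge of the arm |
|---|---|
| Participant | Not blinded (6.4.1.6, 6.6) |
| Investigators, including the principal investigator | Not blinded (6.4.1.6, 6.6) |
| Second dermatologist who scores | Nothing; no masking planned (6.7) |

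The stated reason covers the first two rows. It does not address the third.

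**Inputs.** 12 per group (Section 9.2). Section 6.4.1.1 gives 20 participants in total, which at 1:1 is 10 per group. A 20% loss, the rate mentioned in Section 9.1, would leave 12 × 0.8 = 9.6 per group. Results are therefore shown for 12 and 10. HiSCR is defined in Section 6.4.1.8; HS-PGA and IHS4 are in Appendix 1.

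**HiSCR.** Response needs at least a halving of abscesses plus inflammatory nodules, with no rise in abscesses or draining fistulas. The protocol gives no baseline count, so 4 is an assumption:
- follow-up count 3: (4 − 3)/4 = 25%, not a response;
- follow-up count 2: (4 − 2)/4 = 50%, a response if the other conditions hold.

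Across assumed baselines of 2 to 8, the largest count that still qualifies is 1, 1, 2, 2, 3, 3, 4. One lesion more gives reductions of 0%, 33%, 25%, 40%, 33%, 43% and 38%, all failures. So at every baseline in this range, a participant at the threshold changes status on one lesion. Each change moves the arm's response rate by 1/12 = 8.3 points, or 1/10 = 10 points with 10 per arm.

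**HS-PGA.** Calling a sole inflammatory nodule non-inflammatory moves the score from 2 to 1. With one abscess and one inflammatory nodule, calling the abscess a nodule moves it from 3 to 2.

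**IHS4.** Weights are 1 for a nodule, 2 for an abscess and 4 for a draining tunnel. Calling a tunnel a nodule changes the score by 4 − 1 = 3; not counting it changes the score by 4. Moderate (4–10) becomes mild (3 or less) for totals of 4–6 in the first case and 4–7 in the second. This applies only to participants with a tunnel, and Hurley stage I excludes sinus tracts.

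**Effect on a test between arms.** Assumptions: no true effect, a differential scoring shift of b standard deviations, and a two-sided 0.05 two-sample t test (the groups are different people). The statistic follows a noncentral t distribution with 2n − 2 degrees of freedom and noncentrality b × √(n/2). For n = 12 and b = 0.5 this is 0.5 × √6 = 1.22.

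| Assumed shift (SD) | False-positive rate, 12 per arm | 10 per arm |
|---|---|---|
| 0 | 5% | 5% |
| 0.25 | 9% | 8% |
| 0.5 | 22% | 19% |
| 0.75 | 42% | 36% |

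These rates show sensitivity to a shift. They are not an estimate of any shift in this trial.

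**The case against.** The strongest reply is that masking may not work. The sentence on faint scars describes FUE as used in hair transplantation. The procedure aims to remove follicles completely, both sides are treated, and people without terminal hair in the target area are excluded. A dermatologist examining the axillae or groins at Weeks 6, 12 and 24 may simply see that hair is missing; early healing or a participant's remark may also give the arm away. This stands. A reader might infer that the bias is wholly avoidable, but the documents support only that it can be reduced.

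Three other stronger readings are tempting and not supported:

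- **That both scorers are known to be unblinded.** This is explicit only for the principal investigator. The second dermatologist is not called an investigator, and that person's knowledge of the arm is not stated. What can be said is that no masking is provided.
- **That the principal investigator scores their own surgery.** Section 6.7 does not say which investigator operates.
- **That there will be two score sets, with the preferred one chosen afterwards.** The wording of Section 6.7 could also mean joint scoring, and the rule for combining raters is commonly left to the analysis plan.

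It is also fair to say that this is a pilot which discloses its lack of blinding, and that nothing in it shows the direction or size of any scoring tendency. That lowers the urgency. It does not remove the point, because the between-arm hypothesis rests on these scores.

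**Conclusion.** The point holds in limited form. The protocol masks neither lesion scorer, and its stated reason does not explain why a separate assessor could not be kept unaware of the arm. Lesion counts, HiSCR, IHS4 and HS-PGA are exposed to detection bias in the between-arm comparison. Pain and diary flares come from the participant, who knows the arm whatever the assessor knows, and histology does not depend on lesion scoring.

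The size of the bias is unknown. The 8.3-point change per reclassified participant follows from 12 per arm; that one lesion is enough is illustrated under an assumed baseline of 4. The false-positive rates depend entirely on the assumed shifts. The change is worth making because it is inexpensive and cannot be made after the visits have happened, but the absence of masking does not by itself invalidate the pilot.

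**What to change.** Amend Section 6.7 along these lines:

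> The second dermatologist takes no part in treatment, is not told the allocation and does not consult the treatment record. Participants are asked not to disclose their arm. This assessor scores independently of, and before, the principal investigator at Weeks 0, 6, 12 and 24; at Week 0, scoring is completed before any FUE. These scores are the data of record. The principal investigator's scores are used for agreement and sensitivity analysis. At Week 24 the assessor records a guess of the arm.

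The Week 0 order needs stating because Section 6.4.2.2 lists FUE ahead of the severity scores; without it, a baseline could be taken on freshly treated skin, which would also reveal the arm. Sections 6.4.1.6 and 6.6 should then limit the statement on blinding to participants and to investigators other than this assessor.

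Cost: no new rater, provided the second dermatologist can be kept out of treatment, which the protocol does not confirm. Visit order must be organised, and access to the treatment record at the same clinic restricted. Masking stays partial, since missing terminal hair or early healing may reveal FUE; the recorded guess will help show how far it held.

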## 7. STUDY POPULATION

This study will enroll male and female patients aged ≥18 years who are diagnosed with mild to moderate HS.

The study will consist of 24 recruited participants.

**Study Name:** Hidradenitis suppurativa treated with follicular unit excision: A 24-week prospective study

**Protocol Number:** FUEHS001

**Version & date:** version 1.3, dated 3rd February 2024

## 7.1 RECRUITMENT PROCEDURE

Participants will be recruited through Sinclair Dermatology.

## 7.2 INCLUSION CRITERIA

Participants eligible for inclusion in the study must fulfil all the following criteria:

1. Male and female patients with HS aged  $\geq 18$  years.
2. Mild-moderate HS defined by Hurley stage 1 up to 2A
3. Minimum diagnosis of 3 months prior to baseline
4. Active HS present for at least 3 months from initial diagnosis.

## 7.3 EXCLUSION CRITERIA

Participants fulfilling any of these criteria are not eligible for inclusion in this study:

1. Current treatment with antibiotics, retinoids, immunosuppressants or biologic agents at the discretion of the investigator/research team.
2. Extensive scarring.
3. Absence of terminal hairs in target areas.
4. Previous laser hair removal in target areas.
5. Pregnant or lactating women.

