### 5.3 BACKGROUND INFORMATION

HS was once considered a disease of the apocrine gland, but newer evidence firmly implicates direct follicular involvement in disease pathogenesis. Over 95% of early lesions (< 3 days old) include

hyperkeratosis, occlusion of the follicular unit and an associated perifolliculitis. These are often accompanied by dilatation of the hair follicle (HF) and subsequent stasis in both the apocrine and eccrine glands. While apocrine stasis, hyperplasia and a periglandular inflammatory infiltrate are observed in and around the apocrine glands in 33–90% of cases of HS, they are universally accompanied by extensive inflammation of the HF, eccrine gland and cystic structures, and are thought to be a secondary phenomenon. It has recently been observed that there is a thinning of the basement membrane zone around the junction between the HF and sebaceous gland in HS skin. This area of weakness may predispose to rupture of the hair follicle and spillage of its contents into the dermis and a subsequent inflammatory response. Furthermore, the identification of free keratin filaments in the dermis supports that mechanism and is consistent with follicular rupture playing a key role in disease pathogenesis.

The management of HS is currently multifactorial. Lifestyle changes e.g., smoking cessation and weight loss can reduce the frequency of HS flares. Other lifestyle modifications such as wearing loose clothing may reduce the severity of flares. Systemic therapy includes antibiotics, hormonal therapy e.g. spironolactone, retinoids and immunosuppressants. However, the disease often recurs following therapy interruption or discontinuation. The tumour necrosis factor- $\alpha$  inhibitor adalimumab is a relatively effective treatment, with 41.8-58.9% of adult patients achieving satisfactory clinical response. In chronic refractory cases, surgery, including deroofing and incision and drainage or ablative lasers may be used. Therefore, early intervention is critical to prevent progression of disease to a disfiguring recalcitrant stage.

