##### 6.4.1.3 CONCOMITANT TREATMENT

All treatments administered during the 6 months prior to start of study treatment (including any treatment started during the screening period) will be collected.

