#### 6.4.2 STUDY SCHEDULE

A table of the visits schedule and study procedures is in Appendix 2.

Randomisation will occur prior to recruitment of participants.

The Investigator or his/her approved designee must explain the nature of the study protocol and associated risks to the potential study participant. The potential participant must be allowed to review the study information and to ask questions before being asked to sign the Informed Consent Form.

Signed informed consent must be provided by the potential study participant prior to initiation of any screening evaluations or other study-related procedures. The signature, date, and name of the individual at the site who obtained the informed consent will be recorded in the participant's source record. After written informed consent is obtained, a copy of the signed form will be provided to the patient to keep. The participant will then be assigned a participant number.

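### Exclusion criterion 1 has two wordings that differ for users of the control drug, is not reconciled with the doxycycline allowed before FUE, and may be applied after the arm is fixed

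*Protocol*

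**What the plan says.** **The criterion.** Protocol section 7.3 excludes "Current treatment with antibiotics, retinoids, immunosuppressants or biologic agents at the discretion of the investigator/research team". The Key Exclusion Criteria in the synopsis (section 2) read "Current treatment with systemic antibiotics, retinoids, immunosuppressants or biologic agents at discretion of the investigator". Both texts are current.

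**The treatments.** Section 6.4.1.6 states: "The control group will be managed with topical clindamycin". Section 6.5 lists resorcinol 15% and topical clindamycin as standard care, used as needed at flare. Section 6.4.1.6 also says "Participants may be given medications to prevent flares to stabilize the condition prior to follicular unit extraction" and continues "This may be resorcinol 15% cream and/or oral antibiotics such as doxycycline 100mg". Section 6.4.1.3 collects prior treatment, "including any treatment started during the screening period".

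**The sequence.** Section 6.4.2 requires: "Signed informed consent must be provided by the potential study participant prior to initiation of any screening evaluations or other study-related procedures". It then has a participant number assigned once consent is signed. Section 6.6 ties numbers 1 to 24 to arms before recruitment starts and hands them out in order of recruitment. Eligibility is reviewed at screening (6.4.2.1) and again at Visit 1 (6.4.2.2), up to 28 days later, which is also the visit at which FUE is done. Section 6.4.2.1 says that screening comes before enrolment.

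**The concern.** Three matters meet in one criterion.

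First, the site has two texts for the same patient, and the patients affected are those already on the control drug. In a dermatology clinic that uses this drug as standard care, such patients are likely to present.

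Second, a participant stabilised on doxycycline before FUE is on a current oral antibiotic when criterion 1 is checked at Visit 1. Only undefined discretion decides whether that person stays. The permission is tied to a procedure that only one arm receives, so oral antibiotic use at Week 0 could differ between arms because of how the text is applied and not by chance. Week 0 scores are the baseline for the between-arm comparison in section 6.2, and the direction of any distortion is unknown.

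Third, if the arm is fixed before eligibility is final, a criterion applied at discretion by unblinded investigators can be used after allocation. Randomisation does not protect against that.

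**Working it through.** No sample-size, power or error-rate figure is involved, so the check is a comparison of texts.

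**Step 1: scope of criterion 1.**

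| Patient at entry | Synopsis | Section 7.3 | Section 6.4.1.6 |
|---|---|---|---|
| Current topical clindamycin | Not covered, so eligible | Covered, exclusion at discretion | Is the control treatment |
| Current oral doxycycline | Covered, exclusion at discretion | Covered, exclusion at discretion | Permitted before FUE |

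The first row is a difference between two current texts. Section 5.3 suggests its origin: "Systemic therapy includes antibiotics, hormonal therapy e.g. spironolactone, retinoids and immunosuppressants". The drug classes in criterion 1 overlap closely with that list of systemic agents, so one word has probably been lost from 7.3.

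The second row is a permission and an exclusion that meet at the same visit. Section 6.4.1.6 gives no washout, stop time or exemption from criterion 1. The withdrawal reason in 8.2.1 for medication that may interfere with measurements names no drug and does not settle it.

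**Step 2: order of number and eligibility.**

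- Consent comes before any screening evaluation (6.4.2).
- A participant number follows consent (6.4.2).
- Numbers are linked to arms in advance and given in order of recruitment (6.6). No second numbering is described.
- Eligibility is reviewed at screening (6.4.2.1), then again 0 to 28 days later at Visit 1 (6.4.2.2).

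Read together, the sequence is consent, number (arm fixed), first review, second review. This rests on two assumptions: that the number in 6.4.2 is the allocation number in 6.6, and that recruited means consented. If recruited means enrolled after screening, as 6.4.2.1 permits, at least the first review comes before the arm is fixed. The Visit 1 review remains a question, because the arm must be known at that visit for FUE to be done, and the protocol does not say which comes first on the day.

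**Step 3: how a removal at that stage is classed.** A numbered participant taken out before treatment fits the screening-failure definition in 8.3.4 (consented, study treatment not started). The same person can fit the withdrawal reason for interfering medication in 8.2.1. Section 8.2 asks for a recorded reason only for withdrawals, and 8.4 bars replacement only for withdrawals. The two classes therefore leave different records.

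**Step 4: size.** Baseline antibiotic use is not given, so no effect can be estimated. The only available scale is the arm size: section 9.2 gives 12 per group, so one participant is 1/12 = 8.3% of an arm.

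**The case against.** The strongest reply is that the mismatch is editorial. Both wordings carry a discretion clause, so neither forces a topical user out, and sections 5.3 and 6.5 point to the systemic reading. Any effect on who enters applies to both arms alike. This stands in large part and keeps the wording point small, but discretion does not tell the site which text applies. A reader might infer that the protocol bars users of its own control drug. It does not: 7.3 permits that exclusion without requiring it.

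On doxycycline, a reader might infer either that the protocol is silent or that it contradicts itself outright. Neither holds. Section 6.4.1.6 expressly permits it, and the discretion clause lets permission and exclusion coexist. Section 6.4.1.6 also describes flare treatment as routine care, and section 8.1 allows medication for inflammation without naming an arm. Unequal use between arms is therefore possible but not established. Concomitant medication is collected at every visit, so it would at least be visible.

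On order, allocation is done by a staff member outside the study, screening and Visit 1 may fall on the same day, and nothing says that investigators see the list when they judge eligibility. The unblinding that the protocol describes is attributed to the nature of the treatments. All of this stands. A reader might infer that allocation is unconcealed or that selection bias is built in. The documents do not show that; they leave open two orders, only one of which is safe.

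Reporting of removals by arm may be dealt with in an analysis plan that is not shown. The overlap between screening failure and withdrawal, however, is in the protocol's own definitions.

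**Conclusion.** The point holds in a limited form. It is firm that criterion 1 has two current wordings that differ for users of topical clindamycin, and that nothing reconciles the doxycycline allowed before FUE with criterion 1 at Visit 1 or states the position for controls. It is an inference, resting on the two assumptions in Step 2, that the arm-linked number comes before both eligibility reviews. Post-allocation selection is therefore a risk and not a demonstrated bias.

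It would be tempting to size the risk by removing non-responders from an arm of 12 and recomputing the clinical response rate. That does not fit the mechanism: these removals would happen at or before Visit 1, when response against baseline has not been measured and no one can be known to be a non-responder.

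The severity is minor to moderate. The wording mismatch alone would be minor. The open order of eligibility and allocation, in an open-label trial with 12 per arm and a discretionary exclusion, brings it above that.

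**What to change.** 1. **Section 7.3:** write *systemic antibiotics*, as in the synopsis, and add: *Users of topical clindamycin or resorcinol may enter; use at baseline is recorded.*
2. **Section 6.4.1.6:** permit or bar pre-treatment doxycycline by one rule for both arms, stated as an explicit exception to criterion 1 or as an application of it. If it is permitted, say whether it must have stopped by Visit 1.
3. **Sections 6.4.2 and 6.6:** complete and record the final eligibility review, criterion 1 included, before the arm-linked number is given. The independent staff member keeps the list concealed from investigators until then. Reordering without concealment would protect little, because the list is made in advance and used in sequence.
4. **Sections 8.2.1 and 8.3.4:** report any removal after the number is given by arm with its reason, and not as a screening failure.

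The cost is amendment wording and a small change in the order of steps that already exist: both eligibility reviews and the medication history are in place. The downside is that a procedure slot may have to be held before the arm is known. The existing allowance for screening and Visit 1 on the same day eases this.
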